#### 8.4.2.1. Transaminases

Evaluation of Drug-Induced Serious Hepatotoxicity plots are generated for ALT and AST versus TBL.

The number and percentage of patients meeting the following thresholds, which are consistent with Food and Drug Administration guidance of Drug-Induced Liver Injury: Premarketing Clinical Evaluation (July 2009 Drug Safety), are summarized by the maximum dosage received.

**Table 3: Pre-specified Threshold Levels for Transaminases**

Lab Parameter	Threshold
ALT, AST	$\geq 3 \times$ ULN and $< 5 \times$ ULN
	$\geq 5 \times$ ULN and $< 10 \times$ ULN
	$\geq 10 \times$ ULN and $< 20 \times$ ULN
	$\geq 20 \times$ ULN
	$\geq 5 \times$ ULN for more than 2 weeks
TBL	$\geq$ ULN and $\leq 1.5 \times$ ULN
	$> 1.5 \times$ ULN and $\leq 2 \times$ ULN
	$> 2 \times$ ULN
ALT, AST, TBL	ALT or AST $> 3 \times$ ULN and TBL $> 1.5 \times$ ULN
	ALT or AST $> 3 \times$ ULN and TBL $> 2 \times$ ULN
ALP	$> 1.5 \times$ ULN

Abbreviations: ALP=alkaline phosphatase; ALT=alanine aminotransferase; AST=aspartate aminotransferase; TBL=total bilirubin; ULN=upper limit of normal.

A summary table that includes frequencies and percentages of patients that meet any of the above criteria at any time during the study is provided. A listing of subjects with abnormal ALT, AST, or TBL will also be provided.

#### **8.4.2.2. Frequency of End Stage Kidney Disease, eGFR decline $\geq 30\%$ , or eGFR $< 15$**

The kidney failure composite outcome is defined as reaching one of the following:

- 30% decline from baseline in eGFR; or
- eGFR  $< 15$  mL/min/1.73 m^2; or
- ESKD (initiation of maintenance dialysis or kidney transplant).

A  $\geq 30\%$  decline or eGFR  $< 15$  is considered confirmed when the threshold is achieved at  $\geq 2$  visits. Patients who achieved the threshold at their last visit, and did not have a second confirmatory visit, are considered confirmed. The analysis uses initiation of maintenance dialysis or kidney transplant as reported prior to the end of the follow-up window in the database by the investigator. Any initiation of maintenance dialysis or kidney transplant that occurs after the follow-up window will be listed separately. Patients with a decrease from baseline in eGFR of  $\geq 30\%$  at the last on-treatment visit will be considered to have a  $\geq 30\%$  decrease from baseline eGFR. In the event a patient has both an increase from baseline in eGFR of  $\geq 30\%$  and a decrease from baseline in eGFR of  $\geq 30\%$ , only the decrease from baseline will be considered in composite endpoint analyses.

The proportion of patients with ESKD (dialysis/transplant), eGFR decline  $\geq 30\%$ , or eGFR  $< 15$  will be summarized, and the composite of all these criteria will be evaluated. The frequency analyses will be performed for all visits. No off-treatment eGFR values are included in the analysis.

As a sensitivity analysis, the analyses are repeated for the frequency of patients with ESKD (dialysis/transplant), eGFR decline  $\geq 30\%$ , or eGFR  $< 15$  with all-cause death added to the kidney failure composite.

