 - a. Not expected to reach end stage kidney disease (ESKD) or nephrotic syndrome within 12 weeks of study enrollment, in the investigator's judgement; subjects with eGFR < 20 ml/min/1.73m² should be discussed with the medical monitor before enrollment (eg, such subjects with an average rate of eGFR decline > 1.0 ml/min/1.73m² per month in the 3 months prior to eligibility assessment may not be eligible);
 - b. BNP < 200 pg/mL at the last on-treatment visit in the prior qualifying study or at a new screening visit, if applicable.
 - c. No occurrence of a cardiovascular serious adverse event in the prior qualifying study or in the interval between the end of the qualifying study and the screening visit, if applicable.
3. Willing and able to comply with scheduled visits, treatment plan, laboratory tests, and other study procedures;
4. Evidence of a personally signed and dated informed consent document (and assent form if necessary) indicating that the patient (or a legally acceptable representative) has been informed of all pertinent aspects of the study prior to initiation of any protocol-mandated procedures.

Major exclusion criteria:

1. Participation in other investigational clinical studies involving interventional products being tested or used in a way different from the approved form or when used for an unapproved indication;
2. Patients who have an ongoing SAE from a clinical study that is assessed by the investigator as related to bardoxolone methyl;
3. Unwilling to practice acceptable methods of birth control (both males who have partners of childbearing potential and females of childbearing potential) while screening, taking study drug, and 30 days after the last study drug dose;
4. Women who are pregnant or breastfeeding;
5. Patient is, in the opinion of the investigator, unable to comply with the requirements of the study protocol or is unsuitable for the study for any reason;
6. Known hypersensitivity to any component of the study drug.

Investigational product, dosage, and mode of administration:

Bardoxolone methyl will be administered at oral doses of 5, 10, 20, or 30 mg

Reference therapy, dosage, and mode of administration:

None.

Criteria for evaluation:

Safety: Results of physical examination, laboratory results, ACR, vital sign measurements, weight, AEs, and SAEs.

Statistical methods:

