9.1.9. End Stage Kidney Disease

Patients approaching ESKD should be closely monitored by the investigator to fully characterize their progression. For patients with $eGFR \leq 15.0$ mL/min/1.73 m², initiate more frequent follow-up to closely monitor safety assessments (ie, clinical chemistry (including eGFR), hematology, vital sign assessments (including weight), BNP and N-terminal prohormone B-type natriuretic peptide (NT-proBNP)). Similar frequent follow-up may also be implemented for patients with $eGFR > 15.0$ mL/min/1.73 m² who, in the investigator's opinion based on the anticipated progression of their disease, may be approaching ESKD. Patient follow-up should be completed in-person or through a home health visit where in-person visits are not feasible, at least once every 4 weeks (± 2 weeks), until one of the following occurs:

- Initiation of dialysis;
- Receipt of transplant.

Upon initiation of dialysis, study drug should be temporarily interrupted. Because laboratory and vital sign assessments can be affected by receiving dialysis, those safety assessments should not be performed concurrently while a patient is receiving dialysis. Patients receiving dialysis should continue to be followed for vital status and SAEs by phone or in-person according to the protocol scheduled visits. Dialysis not lasting at least 12 weeks will be considered acute dialysis, and patients should be considered for re-initiation of study drug with medical monitor approval.

After completing acute dialysis, such patients should continue to undergo frequent follow-up (ie, at least once every 4 weeks [± 2 weeks]) while $eGFR \leq 15.0$ mL/min/1.73 m². Study drug may be restarted following acute dialysis, with medical monitor approval. Dialysis lasting at least 12 weeks will be confirmed as maintenance dialysis. Upon confirmation of maintenance dialysis, study drug should be permanently discontinued. Upon receipt of kidney transplant, study drug should be permanently discontinued. See Section 8.5 for description of follow-up options following permanent study drug discontinuation. Initiation of dialysis (acute and/or maintenance) and receipt of kidney transplant due end stage kidney disease should be considered important medical events, and therefore recorded as SAEs.

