### **4.3. Sample Size Considerations**

The 402-C-1803 study is not powered to show efficacy or safety effects, and there is no placebo comparator in this open-label trial. Patient numbers are determined by those who are participating (or who have previously participated) in a qualifying clinical study with bardoxolone methyl and meet eligibility criteria.

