## 8. SAFETY AND TOLERABILITY

Safety and tolerability are evaluated by AEs, SAEs, clinical laboratory test results, body weight, vital signs, and physical examination. All analyses of the safety data are performed using the safety analysis set. Descriptive statistics are presented by treatment analysis group (Section 4.5) assignment in the all analysis populations. No formal statistical testing is performed for safety analyses. Any results not included in summaries based on analysis visit window definitions are presented in data listings.

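### SAP 8.4.2.2 can misclassify patients in the kidney failure composite: loose confirmation, no baseline condition on eGFR <15, and an unclear cut-off for dialysis

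*SAP*

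**What the plan says.** SAP 8.4.2.2 defines the composite as a 30% eGFR decline from baseline, an eGFR below 15, or ESKD (maintenance dialysis or transplant).

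- **Confirmation.** Either eGFR threshold is "considered confirmed when the threshold is achieved at" two or more visits. Then: "Patients who achieved the threshold at their last visit, and did not have a second confirmatory visit, are considered confirmed". The section repeats the single-value rule for a ≥30% decrease at the last on-treatment visit. It also states: "No off-treatment eGFR values are included in the analysis".
- **eGFR <15.** No baseline value is required. Inclusion criterion 2a (Protocol synopsis and 8.1) has no lower eGFR limit. A patient below 20 "should be discussed with the medical monitor before enrollment", and the investigator must not expect ESKD or nephrotic syndrome within 12 weeks.
- **Dialysis and transplant.** Events count "as reported prior to the end of the follow-up window in the database by the investigator". The next sentence lists separately any initiation that falls after the window. SAP Table 2 ends that window 35 days after last dose. Protocol 9.1.9 interrupts study drug when dialysis starts and says: "Dialysis lasting at least 12 weeks will be confirmed as maintenance dialysis". Protocol 8.5 and SAP 8.1 use the same 12-week definition.

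The setting is descriptive. SAP 8 says "No formal statistical testing is performed for safety analyses", and SAP 4.3 says "The 402-C-1803 study is not powered to show efficacy or safety effects".

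**The concern.** In a single-arm descriptive study the counts are the result, so the counting rule should separate sustained loss of kidney function from noise and from a low starting point. Three features work against that.

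1. The label *confirmed* covers two low values a few days apart, two low values years apart with recovery between them, and one unrepeated final value. Because off-treatment eGFR is excluded, no post-treatment value can check that final one.
2. A patient who enters below 15 and stays there counts as reaching eGFR <15 without any decline.
3. The two dialysis sentences use different clocks, so two programmers could produce different ESKD counts from the same data.

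The first two features can add events that are not kidney failure on study. The third can remove true ones. ESKD is a sensitive item here: SAP 2 ties the end of the programme to a trial in which ESKD events did not separate between groups.

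**Working it through.** The plan gives no event rate, sample size or within-patient eGFR variability for this composite, so there is no figure to reproduce. Every CV below is an assumption and is shown over a range.

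**Spacing.** In SAP Table 2, Week 1 covers Days 2–10 and Week 2 covers Days 11–21, so two qualifying values can be one day apart (Days 10 and 11). No upper limit on the interval is set.

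**Any two visits versus two consecutive visits.** Inputs: 14 post-baseline visits (Weeks 1, 2, 4, 6, 8, 12 and 24, then seven more at 24-week steps, to Week 24 + 7 × 24 = 192). Independent normal multiplicative error is applied to baseline and to every visit. A visit qualifies if its value is ≤0.7 × measured baseline. The true loss is constant from the first visit.

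| CV | True loss | Any two | Two consecutive |
|---|---|---|---|
| 10% | 0% | 1.5% | 0.4% |
| 10% | 10% | 13% | 5% |
| 10% | 20% | 48% | 29% |
| 5% | 20% | 9% | 4% |
| 8% | 20% | 35.7% | 19.3% |
| 15% | 20% | 64.7% | 44.5% |
| 20% | 20% | 72% | 53% |

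If the 20% loss begins only after Week 24 (CV 10%), the pair is 32% versus 20%.

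**The single last value.** With lognormal error and no true change, P(one value shows a ≥30% decline) = Φ(ln 0.7 / (s√2)), where s = √ln(1 + CV²). At CV 10%, s = 0.0998, so Φ(−0.357/0.141) = Φ(−2.53) = 0.6%. Over CV 8%, 12.5%, 15% and 20% it is 0.08%, 2.1%, 4.5% and 10.1%. With a true 20% loss at CV 10% (normal error), one last value crosses in 17% of patients, and the last two in a row cross in 6%.

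**The full SAP rule** (any two visits, or the last visit alone) against two consecutive visits at least 28 days apart. Lognormal error, no true change, protocol visit schedule:

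| Follow-up to | CV 10% | CV 15% |
|---|---|---|
| Week 48 | 1.1% vs 0.15% | 9.9% vs 2.3% |
| Week 96 | 1.3% vs 0.2% | 11.7% vs 3.4% |
| Week 216 | 1.8% vs 0.4% | 15.5% vs 5.5% |

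At Week 96 the range over CV 8% to 20% is 0.16% to 25.3% versus 0.02% to 9.4%. With a slow true fall reaching 9.0% at Week 96 and CV 10%, the SAP rule counts 4.1% (2.2% from two visits plus 1.9% from the last visit only) against 0.8%. The comparator here is slightly stricter than the rule proposed under the fix, which also accepts a run of closer visits spanning four weeks.

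**Entry below 15.** For a patient steady at 14 with CV 10%, P(one value <15) = Φ(ln(15/14)/0.0998) = 0.755. P(at least two of 10 visits) = 1 − 0.245¹⁰ − 10 × 0.755 × 0.245⁹, which exceeds 99.9%. At CV 15% it is also above 99.9%. With an assumed on-drug rise of 2 it is 78% to 90%. With a rise of 5.5 (the mean increase that Protocol 5.1.1 gives for the Stage 4 CKD trial) it is about 0.1% to 5.6%. Below a baseline of 15/0.7 = 21.4, the <15 threshold is reached before a 30% decline.

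**Dialysis.** 12 weeks = 84 days and the window closes at Day 35. If the last dose is at dialysis start, 84 − 35 = 49 days pass between window closure and the earliest possible confirmation. A start on Day 0–35 that is reported as maintenance on Day 84 or later misses the reporting sentence, yet it did not occur after the window, so the separate listing does not take it either.

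**The case against.** The strongest reply is that this is one descriptive safety output among several. The composite is not in the primary endpoint list (SAP 3.2.1). A reader might infer that it is the only measure of kidney harm, but it is not. SAP 8.4.1.1 to 8.4.2 plan eGFR change by visit with waterfall plots, ACR ratios, ln(ACR)/eGFR and ACR shift tables. The SAE tables capture dialysis and transplant, and 8.4.2.2 shows the components. This stands, and it limits the consequence.

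Counting an unconfirmed final decline can also be a deliberate choice that leans toward showing harm. That is defensible if the count is labelled for what it is; calling it confirmed is not.

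Four other stronger readings do not hold:

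- *An entry eGFR below 15 is itself an event.* The rule needs values below 15 at two visits or at the last one. (Whether Day 1 is a visit for this purpose is not stated.) The 12-week ESKD criterion and an on-drug rise both reduce such cases, and no document shows that anyone entered below 15.
- *Dialysis-defined ESKD is excluded altogether.* That rests on the reporting phrase alone, which may only name the data source. The next sentence sorts by when initiation occurs, which suggests that the initiation date governs. Transplant needs no 12-week wait. A patient nearing dialysis is seen at least every four weeks once eGFR is ≤15 (Protocol 9.1.9), so may already count through that component. The separate ESKD row remains exposed.
- *Stopping the programme created extra last values.* Each patient has exactly one last visit either way.
- *The 48% versus 29% contrast is the expected effect.* It assumes a true 20% loss at every visit from Week 1, whereas Protocol 5 and 5.1.1 describe early eGFR rises.

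**Conclusion.** The concern holds as a risk of misclassification, not as a demonstrated result.

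- **Confirmation** is the firmest part. The any-two rule counts more patients than two consecutive visits in every scenario tried. At CV 10% the contrast runs from about 1.5% versus 0.4% with no true change to 48% versus 29% with a true 20% loss. For the 20% loss, CV 5% to 20% moves it from 9% versus 4% to 72% versus 53%. These figures rest on an assumed CV, independent errors and no on-drug rise. A rise would lower them, mainly in patients coming from placebo.
- **Entry eGFR** is a real gap in the rule. The number of patients affected is unknown and an on-drug rise would reduce it.
- **Dialysis** is a conflict between two adjacent sentences, confined to starts inside the window that are confirmed after it, with a 49-day shortfall if the last dose is at dialysis start. The two sentences must be reconciled.

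No alpha, power or treatment comparison is affected. The change is worth making because it is cheap and the counts are the output, but its importance is modest.

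**What to change.** Amend SAP 8.4.2.2 in three places:

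1. **Baseline condition.** Count the eGFR <15 component only in patients with baseline ≥15. List patients with baseline <15 separately.
2. **Dialysis and transplant.** State that the date of initiation governs inclusion (up to the end of the follow-up window), whenever maintenance status is later confirmed. Show dialysis without 12 weeks of observation as its own category. It will arise because patients who permanently stop study drug complete End-of-Study procedures and withdraw (Protocol 8.5).
3. **Confirmation.** Require two qualifying values at least 4 weeks apart with no intervening on-treatment value above the threshold. Asking simply for consecutive visits 4 weeks apart would not work early on, because scheduled visits from Week 1 to Week 8 are 1 to 2 weeks apart. The proposed wording lets Weeks 4, 6 and 8 confirm a sustained early loss. Report last-visit-only events in their own row, beside the confirmed count and the combined total.

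Cost: a few sentences and some reprogramming, with no new data collection. The confirmed count becomes smaller and the table gains a row, but the combined total keeps every last-visit event in view.

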Study 402-C-0903, titled “Bardoxolone Methyl Evaluation in Patients with Chronic Kidney Disease and Type 2 Diabetes: The Occurrence of Renal Events” (BEACON), was a Phase 3, randomized, double-blind, placebo-controlled, parallel-group, multinational, multicenter study designed to compare the efficacy and safety of bardoxolone methyl to placebo in patients with Stage 4 CKD (eGFR 15 to 29 mL/min/1.73 m²) and Type 2 diabetes. A total of 2185 patients were randomized 1:1 to once-daily administration of the amorphous SDD formulation of bardoxolone methyl (20 mg) or placebo. The primary efficacy endpoint of the study was the time-to-first event in the composite endpoint defined as ESKD (need for chronic dialysis, renal transplantation, or renal death) or cardiovascular death. Similar to prior studies, bardoxolone methyl patients had mean increases in eGFR that occurred by Week 4 of treatment and remained above baseline through Week 48 (overall mean increase of 5.5 mL/min/1.73 m²). In contrast, placebo-treated patients experienced a mean decline in eGFR (-0.9 mL/min/1.73 m², 95% CI -1.2 to -0.5 mL/min/1.73 m²), corresponding to a relative difference between groups of 6.4 mL/min/1.73 m² (95% CI 5.9 to 6.9 mL/min/1.73 m², $p < 0.001$) ([de Zeeuw, 2013](#)).

Patients in Study 402-C-0804 and 402-C-0903 also participated in a four-week withdrawal period following the treatment period. In 402-C-0804, analysis of the change in eGFR from baseline to Week 56 for patients who received study drug for 52 weeks showed that a portion of the increase in eGFR is retained following withdrawal of therapy. Patients treated with 75 and

150 mg of bardoxolone methyl for 52 weeks had eGFR increases from baseline of 4.0 and 4.3 mL/min/1.73 m², respectively, at Week 56. Similar results were observed in BEACON for patients that received at least 48 weeks of treatment. These data support that the longer-term protective and anti-inflammatory effects of bardoxolone methyl may reverse some of the structural remodeling processes in the kidney associated with declining renal function, resulting in sustained eGFR improvement after withdrawal of drug.

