## **6.4. Baseline Definition**

The last measurement on or prior to the date of first study drug administration is considered the 402-C-1803 Day 1 measurement for the calculation of baseline. If baseline is missing, the last available value in prior qualified studies will be used as baseline.

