#### 6.5.4. Visit Windows

**Table 2: Visit Window (Days)**

Analysis Visit	Label	Target Study Day	Analysis Window
0	Day 1	1	1
1	Week 1	7	$2 \leq \text{Study Day} \leq 10$
2	Week 2	14	$11 \leq \text{Study Day} \leq 21$
4	Week 4	28	$22 \leq \text{Study Day} \leq 35$
6	Week 6	42	$36 \leq \text{Study Day} \leq 49$
8	Week 8	56	$50 \leq \text{Study Day} \leq 70$
12	Week 12	84	$71 \leq \text{Study Day} \leq 126$
24	Week 24	168	$127 \leq \text{Study Day} \leq 210$
48	Week 48	336	$308 \leq \text{Study Day} \leq 364$
72	Week 72	504	$476 \leq \text{Study Day} \leq 532$
96	Week 96	672	$644 \leq \text{Study Day} \leq 700$
120, 144, etc.	Week 120, Week 144, Every 24 Weeks Thereafter	Analysis Visit $\times$ 7	$([\text{Analysis Visit} \times 7] - 28) \leq \text{Study Day} \leq ([\text{Analysis Visit} \times 7] + 28)$
FU	Follow-up	28 days after last dose	$14 \leq \text{Days after last dose}^a \leq 35$

a For safety analyses, last dose for patients completing the treatment or permanently discontinuing study drug that occur on the date of last dose or less than 14 days after last dose are considered on treatment.

The safety follow-up is based on days since last dose. If more than one assessment exists during the follow-up after last dose, the one closest to 28 days following the date of the last study drug administration is used for analysis and summary.

If a parameter is assessed or measured more than once within a visit window, the one that is closest to the protocol-scheduled time point (or target study day) is used for the purposes of data analysis and summary. If two assessments are equidistant from a target study day, the earlier assessment is used. If the visit used for analysis includes two assessments on the same day, the average of assessments will be used for non-laboratory parameters. For laboratory parameters, if both an original and retest result are available in the laboratory dataset, the original result will be used and the second (ie, “retested”) result will be ignored. Records from visits not closest to the target study day, and therefore not used in analyses, are presented in by-subject data listings.

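### The kidney failure composite drops off-treatment eGFR but counts dialysis and transplant into the off-drug follow-up window, so it undercounts eGFR threshold crossings for a drug that raises eGFR

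*SAP*

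**What the plan says.** SAP 8.4.2.2 defines a composite of three components: "30% decline from baseline in eGFR", eGFR below 15 mL/min/1.73 m², or ESKD (maintenance dialysis or transplant). For the two eGFR components it adds: "No off-treatment eGFR values are included in the analysis". For ESKD it takes events "as reported prior to the end of the follow-up window in the database by the investigator", and lists later ones separately. The only sensitivity analysis adds all-cause death. No reason is given for excluding off-treatment eGFR.

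SAP Table 2 sets the follow-up window at 14 to 35 days after last dose, with a target of 28 days. By its footnote, assessments "less than 14 days after last dose are considered on treatment". SAP 6.4 defines baseline thus: "The last measurement on or prior to the date of first study drug administration is considered the 402-C-1803 Day 1 measurement". If that is missing, the last value from the prior study is used.

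On the drug effect, Protocol 5.1.1 says of BEACON that "bardoxolone methyl patients had mean increases in eGFR that occurred by Week 4 of treatment and remained above baseline through Week 48". The same section says that only part of the BEAM rise was retained four weeks after stopping.

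**The concern.** Within one composite, a patient who starts maintenance dialysis 20 days after the last dose is counted, while a patient whose eGFR is first seen to be 30% below baseline on that same day is not.

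For many drugs this would be a minor choice. Here the drug moves the measurement. An on-drug eGFR contains a rise that partly disappears on stopping, and it is compared with a Day 1 value that is drug-free for patients who came from placebo. Some patients whose kidney function has fallen past the threshold without the drug's reversible effect will not cross it on drug.

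At stake is a safety frequency that is biased downwards. The study is descriptive and tests no hypothesis, so alpha and power are not affected. The question still matters: SAP section 2 records that AYAME showed no separation in ESKD events and that development was then stopped.

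**Working it through.** The plan states no expected frequency for this composite, so there is no planned figure to reproduce. The check is threshold arithmetic.

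**Inputs (mL/min/1.73 m²)**
- BEAM, Protocol 5.1.1: mean rise 7.4 at Week 52; retained at Week 56, 4.0 (75 mg) and 4.3 (150 mg). Part that reverses: 7.4 − 4.3 = 3.1 to 7.4 − 4.0 = 3.4. This is approximate, because it sets a mean over treated patients against two dose groups.
- BEACON, Protocol 5.1.1: +5.5 on drug and −0.9 on placebo, so 5.5 − (−0.9) = 6.4, as the protocol states.
- EAGLE baseline eGFR: not given. Drug-free values of B = 30 and B = 50 are assumed.
- The on-drug lift E is assumed additive and constant.

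**Drug-free baseline.** The observed on-drug loss is the drug-free loss minus E/B. An observed 30% therefore needs a drug-free loss of 30% + E/B.

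| E | B = 30 | B = 50 |
|---|---|---|
| 3.1 | 30 + 10.3 = 40.3% | 30 + 6.2 = 36.2% |
| 3.4 | 30 + 11.3 = 41.3% | 30 + 6.8 = 36.8% |
| 6.4 | 30 + 21.3 = 51.3% | 30 + 12.8 = 42.8% |

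Conversely, a patient with a drug-free loss of exactly 30% reads on drug as 30% − E/B: 19.7%, 18.7% and 8.7% at B = 30, and 23.8%, 23.2% and 17.2% at B = 50. None reaches the threshold.

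**eGFR below 15.** The drug-free value must be below 15 − E: 11.9, 11.6 or 8.6.

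**On-drug baseline.** If baseline was itself taken on drug, it equals B + E. An observed 30% decline on drug then needs a drug-free loss of 30% × (1 + E/B). For E = 3.1 and 6.4 this is 33.1% and 36.4% at B = 30, and 31.9% and 33.8% at B = 50, so there is little masking. An off-drug value with no real loss would show an apparent decline of E/(B + E): 3.1/33.1 = 9.4% and 6.4/36.4 = 17.6% at B = 30; 3.1/53.1 = 5.8% and 6.4/56.4 = 11.3% at B = 50. The proposed analysis must guard against this.

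**The case against.** The strongest reply is that kidney safety is well covered elsewhere. SAP 8.4.1.2 summarises eGFR change by visit window, with waterfall plots, and Table 2's windows include follow-up. SAP 8.4.2 plans ACR shifts from baseline to follow-up. Dialysis and transplant are recorded as SAEs. This stands: a reader might infer that the composite is the only kidney-harm outcome, and it is not. What is missing is narrower, namely any planned count of patients who cross the 30% or 15 thresholds off drug.

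The composite also has rules that raise the count. A decline of at least 30% at the last on-treatment visit counts without confirmation, values up to 13 days after last dose are kept, and running ESKD into follow-up captures more events. So it cannot be said that the composite can only reassure falsely, nor that patients stopped for falling eGFR lose their data: their on-drug values remain.

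A reader might also take CARDINAL's 9.5 (Protocol Table 3) and conclude that losses of 30 + 9.5/50 = 49% or 30 + 9.5/30 = 61.7% are needed. That treats the whole rise as reversible, against the protocol's own withdrawal data. At baseline 30 it also adds 9.5 to a drug-free value of 0.7 × 30 − 9.5 = 11.5, which rests entirely on a constant additive effect.

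Finally, it is tempting to suppose that after the 10 May 2023 termination most remaining patients would have a value in the window. The documents give no such count. Protocol Table 5 asks for an End-of-Study visit, if possible within 30 days of discontinuation. A visit before day 14 counts as on treatment, and one after day 35 misses the window.

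**Conclusion.** The point holds. The components have different ascertainment periods, and the on-treatment restriction biases the eGFR components downwards against a drug-free baseline. A 30% on-drug decline corresponds to a drug-free loss of about 36–41% if only the part that reversed in BEAM is counted. That is the portion a four-week off-drug value could be expected to reveal. With the full BEACON difference it is about 43–51%. Larger losses are still counted.

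These figures rest on an additive effect, assumed baselines of 30 to 50, and effect sizes borrowed from diabetic CKD trials. Masking is clearest for Placebo → Bard. For Bard → Bard it depends on the off-drug gap before Day 1, and it is small if the baseline was on drug. The protocol regards the eGFR rise as a true improvement, so loss here means loss measured without the drug's reversible effect.

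This is a cheap improvement to a descriptive safety table. It does not invalidate the plan.

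**What to change.** Keep the on-treatment composite as it is. Beside the all-cause-death sensitivity analysis, add one that also uses eGFR from the 14–35 day follow-up window, so that all components run to the same point. Report n (%) with a decline of at least 30% and n (%) with eGFR below 15 at that visit, by treatment analysis group, with the number of patients who have a value in the window. Flag or exclude patients whose baseline was on drug. State the ascertainment period of each component and how the two-visit confirmation rule applies to a single follow-up value. Keep the SAP 8.4.1.2 rule that eGFR after dialysis or transplant is missing.

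The cost is one repeat of a planned table on data already scheduled for collection. The downsides are incomplete data in the window and, if on-drug baselines are not handled, apparent declines that reflect only withdrawal of the drug.
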